[Part 2 of 2 of the document. The other parts are not shown.]

The number and proportion of patients with medication failures will be summarized by study phase and treatment group in the FAS overall and by visit. A patient will be counted as a medication failure at each visit occurring on and after the date in which a patient is considered a medication failure. Statistical methods described in Section 7.1.1 will be implemented for observed data only. LOCF and missing data imputation will not be performed.

Sponsor: Boston Pharmaceuticals, Inc.  
Protocol Number: BOS161721-02  
SAP Version and Date: Version 3.0, 13Nov2020

The denominator is the number of patients in FAS (overall analysis) and the number of patients with non-missing visit data (for the by visit analysis).

Statistical testing data will be omitted from MAD Phase 1b treatment group displays.

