## 13. APPENDICES

### 13.1. COVID-19 Impact and Data Handling

The COVID-19 Pandemic resulted in contingency plans for BOS161721-02.

- **Safety Oversight:** In case a patient cannot return to the study site for the scheduled visit, the site staff will contact the patient remotely for safety follow up, for example, via telephone or video conferencing. The analysis of safety data will include all collected data regardless of remote data collection.
- **Central Laboratory:** In the case of courier issues that will prevent the protocol-required laboratory specimens to be sent to the study core laboratory, the site should have the safety laboratory specimens (Hematology, Chemistry, and Urinalysis) sent to their local laboratory for analysis and review by the study physician. The local laboratory data will not be entered into the clinical database or analyzed/presented in data summaries.
- **Investigational Product Dosing:** In cases when dosing cannot be performed during the protocol-designated windows, the Investigator should discuss each case with the Sponsor to determine whether it is a missed visit or whether the dosing can be performed outside protocol windows (as a protocol deviation). A minimum of 2 weeks must be maintained between consecutive doses. Patients who miss more than 2 doses of the study drug (whether consecutive or not) will be discontinued from the study and will undergo assessments as outlined in Section 5.5 of the study protocol (Premature Discontinuation). A sensitivity analysis of SRI-4 response using LOCF for missing data and/or observed case data may be performed to assess the impact of patients that did not follow the original protocol dosing schedule.

An addendum to this SAP will be developed that documents all additional data handling techniques employed to manage COVID impacted data, if needed, prior to database lock and unblinding.

Sponsor: Boston Pharmaceuticals, Inc.  
Protocol Number: BOS161721-02  
SAP Version and Date: Version 3.0, 13Nov2020

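### By-visit medication-failure proportions drop failed patients who have no data at that visit, so the rate of a permanent state can fall and the comparison between arms can be distorted

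*SAP*

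**What the plan says.** Section 7.2.12.1 of SAP v3.0 summarises medication failure overall and by visit.

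- **Numerator.** "A patient will be counted as a medication failure at each visit occurring on and after the date" of failure. Nothing reverses the status.
- **Denominator.** "The denominator is the number of patients in FAS (overall analysis"), but for the by-visit rows it is "the number of patients with non-missing visit data (for the by visit analysis").
- **Missing data.** "Statistical methods described in Section 7.1.1 will be implemented for observed data only", and "LOCF and missing data imputation will not be performed".
- **Testing.** "Statistical testing data will be omitted from MAD Phase 1b treatment group displays". No such exclusion is made for the Phase 2 proof-of-concept (POC) part, so its by-visit comparisons carry the Section 7.1.1 methods.

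Section 7.2.12.2 (Table 4) takes the failure date from the protocol deviation eCRF and counts the failure as an event on that date. Patients who withdraw without failing are censored at withdrawal.

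**The concern.** The two by-visit rules do not fit together. Failure is absorbing, and its date comes from a deviation record rather than from a visit assessment. Once a patient has failed, the status at every later scheduled visit is known. The denominator nevertheless asks whether the patient has data at that visit, and the numerator counts only visits that occur. A failed patient who has left, or who misses the visit, is dropped from both counts although nothing about the endpoint is missing.

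Departure is foreseen. Table 4 provides for withdrawal, and Section 13.1 states: "Patients who miss more than 2 doses of the study drug (whether consecutive or not) will be discontinued from the study".

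Three things follow:

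- The by-visit series can go down, which a cumulative failure rate cannot do.
- The last by-visit row can disagree with the overall row and with the Kaplan-Meier curve in the same section.
- The tested POC comparison depends on who is still attending in each arm as well as on who failed.

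The text seen also does not say which data must be present for a visit to count as non-missing, so two programmers could build different denominators.

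**Working it through.** The plan gives no figure for this endpoint, so there is none to reproduce. All failure and departure rates below are assumptions chosen to show the range. Arm sizes of 88 and 44 are used only for scale. They are 132 FAS patients split 2:1, from Section 3.3 of the superseded v2.0.

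**Formula.** Let n be the patients in the arm, F the cumulative failures, wf the share of failures gone and wn the share of non-failures gone. The by-visit rule gives

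p = F(1 − wf) / [F(1 − wf) + (n − F)(1 − wn)],

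against a true cumulative proportion F/n. If wf = wn, p = F/n and there is no distortion. If wf > wn, p is too low. If wf < wn, p is too high.

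**1. Can the rate fall?** Take one 88-patient arm:

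| Day | Cumulative failures | Failures gone | Non-failures gone | By-visit rule | F/88 |
|---|---|---|---|---|---|
| 30 | 4 | 0 | 0 | 4/88 = 4.5% | 4.5% |
| 60 | 8 | 1 | 1 | 7/86 = 8.1% | 9.1% |
| 90 | 12 | 4 | 2 | 8/82 = 9.8% | 13.6% |
| 120 | 15 | 7 | 3 | 8/78 = 10.3% | 17.0% |
| 150 | 17 | 10 | 4 | 7/74 = 9.5% | 19.3% |
| 180 | 18 | 13 | 5 | 5/70 = 7.1% | 20.5% |
| 210 | 18 | 15 | 6 | 3/67 = 4.5% | 20.5% |

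The rate falls after Day 120 although no failure is reversed.

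**2. Which direction?** Take 18/88 = 20.5% cumulative failure, with counts rounded to whole patients:

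- Half the failures gone, no non-failures gone: 9/79 = 11.4%.
- 75% of failures gone, no non-failures gone: 4/74 = 5.4%.
- Only non-failures gone, 10% or 25%: 18/81 = 22.2% or 18/70 = 25.7%.

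**3. Can it create a difference?** Let both arms have true failure of 20.5% (18/88 and 9/44) and let no non-failures leave. With about 25% of active failures gone (4 of 18), the table shows 14/84 = 16.7%. With about 75% of placebo failures gone (7 of 9), it shows 2/37 = 5.4%. That is 11.3 points apart with no true difference.

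**4. Does it shrink a true difference?** Let true failure be 20% against 40%, with wn = 10% and the same wf in both arms:

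- wf = 50%: 8.8/72.16 = 12.2% against 8.8/32.56 = 27.0%. The difference is 14.8 points instead of 20.
- wf = 75%: 4.4/67.76 = 6.5% against 4.4/28.16 = 15.6%. The difference is 9.1 points.

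Each arm's odds are multiplied by the same factor, (1 − wf)/(1 − wn). The odds ratio therefore stays at (0.4/0.6)/(0.2/0.8) = 2.67 in every case, and the risk ratio rises from 2.0 to 2.2 and then 2.4.

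**5. The two remedies on the data of step 1.** The FAS denominator with status kept gives 18/88 = 20.5% at Day 210. For Kaplan-Meier, treat each departing non-failure as censored just before the visit by which it is gone. Survival is then (84/88)(79/83)(74/78)(70/73)(67/69)(65/66) = 0.790, so cumulative failure is 21.0%. Both are non-decreasing. The half-point gap is the effect of counting the six withdrawn non-failures as failure-free.

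**The case against.** The strongest reply is that the by-visit row is a coherent observed-case quantity, namely the status among patients seen at that visit. The cumulative question is already answered by the overall FAS row and by TTMF, with its log-rank test, hazard ratio and curves. On that view the defect is confined to one display of a secondary endpoint, and preferring a cumulative proportion is partly a choice of estimand. The confinement is real and limits the weight of the point. It does not rescue the display: the SAP defines failure as permanent, knows its date independently of the visit, and then applies between-arm methods to a row that discards that knowledge.

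A reader might go further and infer that the by-visit rates are always too low and always shrink a true treatment effect. The documents do not support that. Nothing in the text seen says that failed patients must or tend to leave the study; Section 13.1 ties discontinuation to missed doses. The bias reverses when non-failures leave more often (step 2). Shrinkage under equal departure patterns appears only on the risk-difference scale (step 4), and Section 7.1.1, as worded in v2.0, displays an odds ratio as well as the difference.

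A fair objection also applies to the simplest repair. An FAS denominator at every visit counts each withdrawn non-failure as still failure-free, which is a form of implicit imputation. That is why it is the second choice below.

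**Conclusion.** The point stands as an inconsistency in how the by-visit analysis is built. The v3.0 wording allows the proportion for a permanent state to fall, to disagree with the overall row and the Kaplan-Meier curve, and to distort the comparison between arms. The level is understated if failures leave more often than non-failures and overstated if non-failures leave more often. The between-arm contrast is biased if departure patterns differ.

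The mechanism needs only that some failed patients lack later visit data. Its size is unknown, because the failure and departure rates above are assumptions. That the by-visit comparison is tested is read from the reference to Section 7.1.1 and from the exclusion of testing for Phase 1b only. The v3.0 text of Section 7.1.1 was not available; the v2.0 text specifies Pearson's chi-square at a two-sided 0.10 level. The overall FAS proportion and TTMF are unaffected.

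**What to change.** **Preferred.** Report as the by-visit result, for each arm, the Kaplan-Meier cumulative failure estimate at each scheduled visit day with its 90% confidence interval, from the analysis in Section 7.2.12.2. It keeps every failure, cannot fall, and censors withdrawn non-failures instead of declaring them failure-free. It relies on the usual assumption that withdrawal is unrelated to the risk of failure.

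**Alternative.** Use the FAS as denominator at every scheduled visit and keep each failed patient in numerator and denominator at all later scheduled visits, attended or not. State the downside: withdrawn non-failures are then counted as failure-free, which understates failure somewhat when they leave early.

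**If the observed-case row is kept as well.** Define which data make a visit non-missing, label the row as status among patients observed at the visit, and note that it need not be monotone.

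The cost is one or two sentences in Section 7.2.12.1 and a small change to the table shell. No new data are needed, and the change should be made before unblinding.

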#### 7.2.12.2. Time to Medication Failure (TTMF)

Medication failure is defined in Section 4.6 of the study protocol and discussed in Section 7.1.1. TTMF will be computed as the event date (as described below) – randomization date + 1.

Kaplan-Meier methods will be used to estimate TTMF for each treatment group. Estimates of median TTMF will be provided along with 90% confidence intervals. Q1 and Q3 will also be tabulated. Comparisons between treatment groups will use the two-sided log-rank test. In addition, hazard ratio (HR) estimates with 90% CIs will be calculated from a Cox proportional hazards regression analysis that includes treatment as a factor. Censoring rules are defined as in Table 4.

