### 7.2.13. Duration of Longest SRI-4 Response

Duration of longest SRI-4 response will be computed for patients who have been identified as a responder at least once based on criteria defined in Section 7.1.1. The duration of longest response will be defined as the longest period a patient meets the SRI-4 responder criteria at consecutive visits. This will be computed as the date of last consecutive SRI-4 response – date of first consecutive response + 1.

The duration of longest SRI-4 response will be analyzed using an analysis of variance (ANOVA) model with treatment group as the effect. The p-value for the difference between the BOS161721 and placebo group is based on the F-test.

The mean, SD, median, minimum, maximum, Q3, Q4, LS Mean estimate, its standard error and 90% CI will be tabulated by treatment group and for the difference between treatment groups (BOS161721 versus placebo).

If a patient has missed a visit between two scheduled visits with a response at both, the patient will be counted as having a response at the missed visit unless otherwise specified.

Duration of longest SRI-4 response will be displayed in the SRI response listing.

These analyses will also be performed for the MAD Phase 1b with the exception of the statistical testing.

### 7.2.14. Time to First BILAG A Flare or >1 BILAG B Flare through Day 210

Time to first BILAG A Flare or >1 BILAG B Flare will be computed as the event date (as described below) – randomization date + 1. If a patient is designated as a medication failure prior to or on their day 210 visit, they will be considered as having a BILAG flare (event) as of the date of first dose of the medication leading to the medication failure designation due to prohibited medication or unallowable CS burst.

Time to first BILAG A Flare or >1 BILAG B Flare will be analyzed with Kaplan-Meier methods described for TTMF and censoring as described in Table 5. Kaplan-Meier curves will be plotted over time.

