### 13.3. SLEDAI-2K Index

|   |  |                        |  |
|---|--|------------------------|--|
| Subject Number: _____ - _____   |  |                        | Protocol BOS161721-02  |
| Screening / Randomization / _____ Week Visit & Date of Assessment: _____ - _____ - 20
<small>(Circle visit type &/or enter visit week)</small>       |  |                        | (Day) _____ Month _____ Year _____   |
| SLEDAI 2K Index
Must be present at the time of visit or in the preceding 30 days (or 10 days for V1 and V2) and SLE-Related to be checked! |  |                        |  |
| Wt  | (  ) if Present | Descriptor             | Definitions
If descriptor is checked as present, please check appropriate condition(s) in definition and/or specify in the space provided.   |
| 8   |                            | Seizure                | Recent onset (last 28 days). Exclude metabolic, infectious or drug causes. Specify if checked:  |
| 8   |                            | Psychosis              | Altered ability to function in normal activity due to severe disturbance in the perception of reality. Include:  hallucinations,  incoherence,  marked loose associations,  impoverished thought content,  marked illogical thinking, and  bizarre, disorganized, or catatonic behavior. Exclude uremia and drug causes.   |
| 8   |                            | Organic Brain Syndrome | Altered mental function with  impaired orientation, memory or other intellectual function (with rapid onset and fluctuating clinical features),  inability to sustain attention to environment, and at least 2 of the following:  perceptual disturbance,  incoherent speech,  insomnia or daytime drowsiness,  increased or decreased psychomotor activity. Exclude metabolic, infectious or drug causes. |

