#### 7.2.10. Results and Changes from Baseline in SLEDAI-2K

The SLEDAI-2K is a validated instrument that measures disease activity in SLE patients at the time of the visit and in the previous 30 days. It is a global index and includes 24 clinical and laboratory variables that are weighted by the type of manifestation, but not by severity. The total score falls between 0 and 105, with higher scores representing increased disease activity. The SLEDAI-2K has been shown to be a valid and reliable disease activity measure in multiple patient groups. A SLEDAI-2K of 6 or more generally represents moderately to severely active disease.

The analysis of SLEDAI-2K will be performed using an analysis of covariance (ANCOVA) model with change from baseline to each nominal visit as the dependent variable, treatment group as the factor, and the baseline SLEDAI-2K score as a covariate. The SLEDAI-2K total score is calculated and provided in the clinical database. A missing total SLEDAI-2K score will not be imputed. Observed results only will be presented for the change from baseline analysis.

Sponsor: Boston Pharmaceuticals, Inc.  
Protocol Number: BOS161721-02  
SAP Version and Date: Version 2.0, 29Nov2018

The p-value for the difference between the BOS161721 and placebo groups at each nominal visit is based on the F-test.

Descriptive statistics for the SLEDAI-2K total score will be summarized separately at baseline and each visit. Change from baseline will be summarized at each post-baseline visit. The LS Mean estimate, its standard error and 90% CI will be tabulated by treatment group and for the difference between treatment groups (BOS161721 versus placebo) for change at each visit.

Statistical testing data will be omitted from MAD Phase 1b treatment group displays.

The mean and standard deviation of the change from baseline in observed SLEDAI-2K total score will be presented graphically over time by study phase and treatment group.

SLEDAI-2K observed results will be presented in a data listing for all randomized patients.

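### The Cox models for medication failure and flare, and the ANOVA for response duration, use treatment alone; adding baseline SLEDAI-2K would bring a modest efficiency gain at little cost

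*SAP*

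**What the plan says.** The models at issue are in SAP Version 3.0 (13Nov2020):

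- **7.2.12.2, time to medication failure.** The test is fixed first: "Comparisons between treatment groups will use the two-sided log-rank test". The Cox model is an addition that supplies an estimate: "hazard ratio (HR) estimates with 90% CIs will be calculated from a Cox proportional hazards regression analysis that includes treatment as a factor". No other model term or stratification factor is named.
- **7.2.14, time to first BILAG flare.** This endpoint "will be analyzed with Kaplan-Meier methods described for TTMF and censoring as described in Table 5", so it inherits the same log-rank test and the same Cox model. Medication failure also counts as an event here (Table 5).
- **7.2.13, duration of longest SRI-4 response.** This "will be analyzed using an analysis of variance (ANOVA) model with treatment group as the effect", and it is computed only "for patients who have been identified as a responder at least once".

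Baseline disease activity is available. The SLEDAI-2K form in Appendix 13.3 of Version 3.0 carries the visit label "Screening / Randomization".

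Version 3.0 is shown only from the end of 7.2.12.1 onward, so for earlier sections Version 2.0 (29Nov2018) is the evidence at hand. There, Section 7.2.10 models change in SLEDAI-2K with "treatment group as the factor, and the baseline SLEDAI-2K score as a covariate". Section 7.2.4 uses the Day 0 oral corticosteroid dose to define sustained reduction, so that dose should also be in the database.

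**The concern.** Medication failure and flare may well depend on disease activity and steroid use at entry. Under Version 2.0 Section 7.1.1, medication failure includes raising corticosteroids above a fixed daily ceiling, and a patient who enters close to the ceiling has less room below it. Through Table 5 the same link carries into time to flare. SRI-4 requires a fall of at least 4 points from the baseline SLEDAI-2K, so the baseline score also bears on who can respond and for how long. None of these links is quantified in the documents.

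Leaving a prognostic covariate out of a Cox model moves the estimated hazard ratio toward 1 relative to the ratio conditional on that covariate. In a linear model it leaves residual variance that could have been explained. At stake is the efficiency of three secondary analyses, and how well the reported hazard ratio describes the effect in patients with the same baseline activity.

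**Working it through.** **The plan's own figure.** The only power statement is for the primary endpoint (Version 2.0 Section 3.3): 132 patients, 2:1, 65% versus 40%, two-sided 10%, power above 80%.

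- Pooled proportion: (44 × 0.40 + 88 × 0.65)/132 = 74.8/132 = 0.567.
- Standard error under the null: √[0.567 × 0.433 × (1/44 + 1/88)] = 0.0915. Under the alternative: √[0.24/44 + 0.2275/88] = 0.0897.
- Power = Φ[(0.25 − 1.645 × 0.0915)/0.0897] = Φ(1.11) = 86.6%. Exact enumeration gives 86.3%; with continuity correction it is 82.9%.
- 132/(1 − 24/156) = 156, as stated.

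The figure reproduces, but it does not bear on the models discussed here. No power is stated for them.

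**Cox models.** From the documents: 88 versus 44 patients (132 at 2:1) and two-sided 10%. Assumed: true hazard ratio 0.5; exponential times; follow-up to Day 210; 15% random early censoring; placebo event rate of 25% or 50% by Day 210; one standard-normal baseline covariate. There were 3,000 simulated trials per row, so the simulation error is at most √(0.25/3000) = 0.9 points per power value.

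| Mean events | Covariate HR per SD | Log-rank power % | Cox, treatment only % | Cox, adjusted % | Cox gain (points) | Median HR, unadjusted / adjusted |
|---|---|---|---|---|---|---|
| 21.2 | 1.0 | 48.3 | 46.6 | 46.8 | +0.2 | 0.501 / 0.500 |
| 21.0 | 1.25 | 49.9 | 48.9 | 48.3 | −0.6 | 0.492 / 0.489 |
| 21.3 | 1.5 | 49.9 | 48.6 | 48.9 | +0.3 | 0.498 / 0.492 |
| 21.6 | 2.0 | 44.9 | 43.5 | 47.2 | +3.7 | 0.529 / 0.502 |
| 44.5 | 1.0 | 73.8 | 73.4 | 73.5 | +0.1 | 0.501 / 0.499 |
| 44.8 | 1.25 | 74.1 | 73.4 | 73.9 | +0.5 | 0.501 / 0.494 |
| 45.3 | 1.5 | 71.8 | 71.0 | 73.9 | +2.9 | 0.517 / 0.502 |
| 46.1 | 2.0 | 68.0 | 67.4 | 75.9 | +8.5 | 0.534 / 0.494 |

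Set against the planned log-rank test rather than the unadjusted Cox test, the adjusted test differs by −1.6 to +2.3 points with about 21 events and by −0.3 to +7.9 points with about 45.

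With no treatment effect (hazard ratio 1.0, about 62 events, covariate HR 1.0, 1.5 and 2.0 per SD), rejection was 9.7%, 9.4% and 9.1% unadjusted and 9.7%, 9.2% and 9.6% adjusted. Neither model inflates the 10% level.

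The simulation recorded power and the median hazard ratio, not interval width, so nothing is claimed about the 90% CI becoming narrower. It also had one covariate only.

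**Duration.** If baseline SLEDAI-2K correlates ρ with duration within group, adjustment multiplies the residual SD by √(1 − ρ²). Suppose the unadjusted power is 70% (assumed). Then power = Φ[(1.645 + 0.524)/√(1 − ρ²) − 1.645], which gives 70.4% at ρ = 0.1, 73.5% at 0.3 and 80.5% at 0.5.

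**The case against.** The case for leaving the plan alone is substantial, and most of it stands.

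- **Lost power.** A reader might infer that the plan gives away power and that a Cox covariate recovers it. The planned comparison is the log-rank test, and the Cox model only adds an estimate. A covariate in the Cox model alone leaves the planned p-value unchanged. The power gains belong to a test the SAP does not name, so the change must name one.
- **Inconsistency.** A reader might see a contradiction with the baseline-adjusted continuous endpoints. There is none. Those ANCOVAs adjust a change score for the same instrument's own baseline, and times to event and response duration have no such value. The primary SRI-4 analysis in Version 2.0 is itself an unadjusted chi-square test.
- **Bias from chance imbalance.** Random imbalance in baseline activity is already covered by randomization and the confidence interval. It is not bias, and the null rejection rates above bear this out.
- **Unseen text.** Version 3.0 Section 4.1 is not shown. Version 2.0 Section 4.1 allowed exploratory analyses of uncontrolled factors. That would permit an adjusted model but would not pre-specify one.
- **Size.** Event rates, hazard ratio and prognostic strength are all assumed. Over much of the range the gain is within simulation error.

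What survives is that the current text names treatment only, a plausible prognostic score is already collected, and a covariate chosen after unblinding would be post hoc.

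**Conclusion.** This is an efficiency improvement to secondary analyses, not an error. The time-to-event comparisons are valid without adjustment. If baseline activity is prognostic, the unadjusted hazard ratio sits closer to 1 than the conditional one: 0.53 against 0.49 in the strongest case examined.

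The gain in Cox power is about 0 to 9 points with about 45 events and about 0 to 4 with about 21, and near zero for a weakly prognostic score. Both ranges rest on an assumed hazard ratio of 0.5, assumed event rates, and the Version 2.0 sample size. For duration the gain is about 0.4 to 10 points at ρ from 0.1 to 0.5, given an assumed starting power of 70%.

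Restricting the duration analysis to patients who responded at least once selects on a post-randomization outcome. That is a separate and larger limitation, and baseline adjustment does not cure it. Version 2.0 Section 4.3 applies no multiplicity adjustment, which also argues for treating this point as minor.

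**What to change.** Before unblinding, amend the SAP as follows:

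1. In 7.2.12.2 and 7.2.14, add baseline SLEDAI-2K total score to the Cox model as a continuous covariate. Add Day 0 oral corticosteroid dose only if the blinded event count allows: with about 21 events, three terms leave 21/3 = 7 events per term, and with about 45 they leave 15.
2. Report the adjusted Wald or score test, or a log-rank test stratified by baseline SLEDAI-2K category with the cut-point stated in advance, alongside the planned two-sided log-rank test.
3. Keep the unadjusted hazard ratio as a sensitivity analysis.
4. In 7.2.13, add baseline SLEDAI-2K to the model, and state that the comparison is limited to responders and that adjustment does not restore the randomized comparison.

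The cost is SAP wording and slightly more analysis work. The hazard ratio becomes conditional on baseline activity and should be labelled so. No new data are needed for baseline SLEDAI-2K.
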